6. STUDY PROCEDURES

After providing written informed consent, all subjects will complete a clinical diagnostic interview via a virtual visit with a board-certified study clinician to assess eligibility. A study clinician will complete the Reproductive Potential Form. All subjects will be administered an assessment battery including a brief demographic interview and the SRS-2 (Pre-Screening). If an additional family member of the subject is available, we will ask that family member to independently complete an SRS-2 form. Both forms will be scored and the form with the higher score will be used to determine subject eligibility in order to reduce the possibility of under-recognition of social impairment.

We anticipate that subjects may enter this study following completion of/withdrawal from other ASD protocols in our office, and that there may be procedural overlap. So as to not burden subjects/parents/guardians with redundant time commitments, we will use the following diagnostic data previously collected: If a subject has completed an evaluation with one of the study clinicians and/or the structured diagnostic assessment in the three years prior to entrance into this study, he/she will not be asked to repeat any overlapping diagnostic procedures. We will use the study diagnostic data that had been previously collected so as to not burden the subject with redundant time commitments.

However, the study clinician will review the interval time period to assess for clinically significant medical or psychiatric history, to ensure that the subject meets appropriate study entrance criteria.

All female subjects of childbearing potential will have a urine pregnancy test that will be mailed to their address prior to Screening visit. If a participant has a positive urine pregnancy test, she will not be able to take part in the study. The study doctor will inform the participant of any positive test results.

Upon completion of Informed Consent, subjects will be randomized to receive either tPBM or sham and the respective device will be mailed. This study will include up to 27 subjects randomized at 1:1 ratio into 2 groups: tPBM and Sham.

Treatment group assignment will be decided by randomization and managed by the study statistician. Randomized codes will be generated by the study statistician. When the study statistician is not available, randomization will be managed by the department's clinic manager. For each randomized subject, a sealed envelope with treatment assignment will be available at the study site. Both subjects and study staff (except the study statistician and clinic manager) will be blind to treatment group assignment. The sham treatment will consist of applying all the procedures for the delivery of tPBM, while actually delivering no light. The blinding of the sham will be effective because the radiation is not visible, and because the active therapy will not produce any patient discernable difference from sham, e.g., skin warming. The sham treatment will mimic tPBM procedure as described below (Devices and Dosing).

All participants will receive daily tPBM/sham treatments for 8 weeks. All subjects and investigators (except the study statistician) will be blind to treatment sequence assignment.

Subjects will be assessed on measures of efficacy and safety at regular scheduled visits throughout the study. Study clinicians will complete a chart note at Weeks 0, 1, 2, 3, 4, 6, and 8. For a complete schedule of assessments, please refer to Table 2. The screening process may take place over multiple days, as necessary. All study visits will be conducted via Telemedicine platform.

All data will be collected and entered into Research Electronic Data Capture (REDCap), an electronic data capture system that streamlines data collection and ensures data integrity. REDCap software allows researchers to design and implement study surveys electronically for collecting, storing, retrieving, and manipulating data.

Subjects, family members or friend when available, and research staff will enter survey responses into the electronic assessment forms on REDCap. A member of study staff will send forms on REDCap to subjects via the REDCap email function. The responses will be then transmitted securely via an encrypted connection and stored in a secured database. Electronic data capture eliminates the need for subsequent data entry by staff, thus minimizing human error. However, if REDCap is unavailable or malfunctioning, study staff will print or download PDFs of all study instruments and mail or securely email (or email normally if given verbal consent) the instruments to subjects (and optional informants), thus study data will be collected in paper or PDF form.

Subjects will be instructed to administer daily tPBM treatments for 8 weeks. Each subject will be mailed a device to keep at home during study participation and return to study staff upon completion. At the

baseline visit, the subject will be instructed on how to accurately place the device. Written instructions are also provided with the device.

Devices and Dosing

Each subject will receive daily tPBM or sham treatments for 8 weeks.

There will be 10 Niraxx G1 Headbands to allow up to 10 subjects simultaneously receiving treatment at any given time. Five of these devices will be designed to be sham device. The treatment will be bilateral and applied to the frontal areas with application sites on the left side and on the right side [left and right forehead centered on EEG sites on F3, Fp1 and F4, Fp2 and Fz, Fpz]. The probes delivering the LED light are embedded on the inside of the headband and are activated by a button press once accurate placement is ensured (Appendix 1: Niraxx G1 Headband Quick Start Guide). Energy is administered with a radiation wavelength of 850 nm. Following the Week 0 (baseline) study visit, the duration of irradiation is started at 20 min per day for the first three days, increased to 30 min per day on day four of treatment, and to 40 min per day on day eight of treatment. At day 15 (Week 2), the clinician will recommend 50 min daily in the context of good tolerability (Table II). The dose will be escalated to 50 min daily if no side-effects occurred. In the case of an adverse event, the tolerated lower dose will be kept. Therefore, the duration of irradiation is 20-50 minutes at each application site (all sites are irradiated at the same time which is equivalent to 20-50 minutes of total time) (Lampl et al., 2007; Schiffer et al., 2009; Zivin et al., 2009). Each subject will receive specific instructions on appropriate application of tPBM treatment device at the Baseline visit. Written instructions are also provided with the device. All staff who deliver instructions must pass training that is approved by the MGH Laser Safety Committee.

The treatment device is classified as an “Exempt” device in accordance with the requirements of the international standard EN 62471 – Photobiological safety of lamps and lamp systems and, when used correctly, the output is less than the maximum permissible exposure (MPE) no special controls are needed for the environment it is to be used in. At the time of study implementation, the staff will be provided training on basic safety procedures relative to the use of the device. The staff will then instruct the subject on the administration of the tPBM such that the headband is appropriately placed. Written instructions are also provided to the participant with the device. The delivery of the tPBM is expected to last 20-50 minutes total. The subject will be asked to rest for five minutes after the delivery of tPBM. Sites of application will be inspected at each study visit. At all visits, study staff will confirm with the participant that they understand and are following the provided instructions. Trained study staff will review the instructions with participants if it is necessary as to ensure all subjects understand and adhere to instructions.

Flexible Titration Schedule

Titration of tPBM will follow a flexible titration schedule with an option for slower titration, holding at lower dose, or lowering the dose based on tolerability and response to the tPBM as per clinician judgment. Dose will be adjusted upward per the flexible titration schedule provided the treatment is well tolerated. Titration will be adjusted if a participant experiences a treatment limiting side effect related to tPBM, such as scalp discomfort, headaches, or any side effects reported on TSRQ. We will plan to titrate to 50 minutes for all participant unless a participant experiences a side effect at 40 mins, in which case, we will continue at 40 minutes. Week 2 and onwards, participants will be maintained on maximum achieved dose with a one-time option to decrease the dose of the tPBM to the next lowest

available dose per clinician judgment based on tolerability. For the detailed titration schedule, please refer to Table II.

Concomitant Medications/Treatments

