The purpose of this 8-week double-blind randomized placebo-controlled study is to assess the tolerability, safety, and efficacy of tPBM in adult patients with ASD. Based on our central hypothesis that tPBM will be safe, tolerable, and effective in improving ASD symptoms in adults, we propose to enroll up to 27 participants of both genders ages 18-50 years with intact intellectual functions satisfying DSM-5 criteria for ASD.

Primary Aims:

Aim 1. To examine the clinical efficacy and safety of tPBM in patients with ASD. We will study the short- and long-term clinical effects of tPBM in 27 adults with ASD by conducting an 8-week randomized clinical trial (RCT).

Secondary Aim:

Aim 1. Explore anti-inflammatory biomarker response to tPBM treatment. We will examine any relationship to ASD symptom severity before and after the 8-week treatment course.

Aim 2. To study the treatment effect of tPBM on mood, social cognition, executive function, ADHD, depression and anxiety symptoms in adults with ASD.

3. General Description of Study Design

This study is a double-blind, placebo-controlled, sequenced parallel study on the use of tPBM as treatment for ASD symptoms in adult patients. This study will last up to 12 weeks from enrollment (allowing up to four weeks from the date of consent to schedule and complete the initial screening process).

4. Subject Selection

Subjects diagnosed with ASD who meet all inclusion criteria, have none of the exclusion criteria, and are willing to undergo the Informed Consent process will be eligible to participate in this clinical study.

Inclusion Criteria

Subjects may be included in the study only if they meet all of the following criteria:

- Male or female participants between 18 and 50 years of age (inclusive)
- Fulfills DSM-5 diagnostic criteria for autism spectrum disorder as established by the clinical diagnostic interview.
- Participants with at least moderately severity of ASD symptoms as demonstrated by SRS raw score ≥ 85 and CGI-ASD severity score ≥ 4

- Participants must understand the nature of the study. Participants must be deemed not to have impaired decision-making capacity and must have the capacity to provide direct informed consent. Participants must sign an IRB-approved informed consent form before initiation of any study procedures.

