Each subject and the Investigator reserve the right at any time to terminate a subject's participation in the clinical investigation.

Possible reasons for withdrawal or removal from the study may include:

- The subject voluntarily withdraws consent.
- The subject was not eligible based on the study inclusion and exclusion criteria.
- The subject develops an Adverse Event that would not allow continuation in the study.
- The subject has an Adverse Event which in the opinion of the Investigator warrants withdrawal from the study. Niraxx Inc must be notified within two business days.
- A decision is made by the subject and/or Investigator that the subject should be withdrawn from the study.
- Subject death
- Positive pregnancy test

When a subject withdraws or is removed from the study, the following will be performed, if feasible, at the study termination (exit) visit:

- Virtual examination of exposure sites
- Progress Note
- MGH-SECS-C
- AISRS
- HAM-A
- HAM-D
- CGI
- GAF
- CTAE
- Concomitant medications form
- SRS-2
- BRIEF-A
- TSRQ
- MGH-SECS-I
- ABCL
- Q-LES-Q
- ASRS

For all subjects who withdraw from the study prematurely, the date, and reason for withdrawal will be documented.

If study participation is discontinued due to safety reasons, participants will receive three follow-up visits, giving adequate time for appropriate psychiatric care to be arranged.

8. Benefits

There may be no direct benefit to subjects participating in this study. Participants may benefit by potentially experiencing improvement in ASD symptoms and by gaining knowledge about ASD.

Study subjects will receive comprehensive clinical assessment of their psychiatric condition. This information will be readily available to their counselors if the subjects agree to disclose. This information might guide counseling in the long-term treatment. In the short-term, the subject will receive close and systematic monitoring, beyond current standards of care. Easy access to routine physical exams are also a potential benefit in the community population, which is often underserved. The subjects will have access to a different modality of treatment if counseling was not sufficient and if medications were not acceptable to them. However, there may be no improvement at all, or benefit to participant.

9. Statistical Analysis

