54 subjects will be randomized (1:1) into the tPBM or placebo/sham group and be treated for 8 weeks post randomization. This design largely protects against the bias introduced by confounding factors.

We will rely on comparisons of the participants' performances in each study arm (placebo/sham and tPBM) at baseline prior to the initiation of treatment relative to their scores at the last assessment (completion/drop-visit). Since we are following subjects over a short period, missing data are not expected to impact our analyses such that standard statistical analyses will be employed. Specifically, we will employ longitudinal mixed-effects regression models (RM) with random effects for the subjects using Stata 16.0 (StataCorp, 2019). The RMs will use robust standard errors to account for the repeated measures on each subject. We will test binary data using mixed-effects logistic RMs, count data with mixed-effects Poisson RMs, and normally distributed data with mixed-effects linear RMs. Each model will predict outcome scores from treatment group (placebo/sham or tPBM), study visit (continuous predictor), and the treatment group-by-study visit interaction. All analyses will be intent to treat (ITT).

10. Monitoring and Quality Assurance

Consistent with good clinical practice, safety will be monitored at each study visit by a subject's assigned clinician. This clinician will be available 24 hours a day by page. The principal investigator will supervise all study activities including ratings and reported adverse events. All procedures have been designed to minimize subject discomfort, and no subject will be asked to engage in research procedures not outlined in the consent form.

Safety will be monitored through treatment-emergent adverse events. Subjects will be monitored for adverse events at each visit. All adverse events will be recorded. A subject may be dropped from the study or dosage may be decreased at any time due to adverse events. All adverse events will be reported to the PHRC according to PHRC guidelines. All concomitant medications will be assessed at every study visit.

All adverse events will be recorded from the time of Informed Consent through study completion, or termination. The Adverse Event CRF must be completed and submitted to the IRB and Niraxx, as required. Regulations for adverse event handling and reporting contained in the FDA and ICH Guidelines will be adhered to.

Overview and Definitions

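### The number randomised is up to 27 in one section and 54 in another, and the only stated trigger for randomisation is completed consent, with no express condition that screening has confirmed eligibility.

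*Combined protocol and SAP*

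**What the plan says.** **Number.** Section 6 says: "This study will include up to 27 subjects randomized at 1:1 ratio into 2 groups: tPBM and Sham". Section 9 says: "54 subjects will be randomized (1:1) into the tPBM or placebo/sham group and be treated for 8 weeks post randomization". Section 2 plans to enrol up to 27 and to study 27 in the randomised trial. Section 4 (Source of Subjects) plans to enrol up to 54 so that up to 27 are exposed. Section 5 counts a person as enrolled once consent is signed. No section gives an effect size, SD, alpha, power or dropout rate.

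**Timing.** The trigger sentence in Section 6 is: "Upon completion of Informed Consent, subjects will be randomized to receive either tPBM or sham and the respective device will be mailed". The same section says that, after consent, "all subjects will complete a clinical diagnostic interview via a virtual visit with a board-certified study clinician to assess eligibility". One inclusion criterion is "SRS raw score ≥ 85 and CGI-ASD severity score ≥ 4". The CGI is first scheduled at the screening visit, as is the first pregnancy test, and washout follows the screening period. Section 3 allows up to four weeks from consent for screening. Table II places the criteria check at the screening visit and, as extracted, has no row for randomisation.

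**Later ineligibility.** Section 7 (Withdrawal from the Study) gives as one reason for removal: "The subject was not eligible based on the study inclusion and exclusion criteria". It does not say whether this means before or after randomisation. For those removed, "the following will be performed, if feasible, at the study termination (exit) visit". Section 9 declares every analysis intention-to-treat without defining the set.

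**The concern.** Two things are unclear that a trial needs to have fixed: how many people are allocated, and at what moment.

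The first decides how much information the trial can yield. A total of 54 is twice 27, and nothing in the plan shows which figure the analysis was built on.

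The second decides who belongs to the randomised set. If the trigger were followed to the letter, people would be allocated and sent a device before the interview and ratings that establish eligibility. Those who then failed would go one of two ways. If kept in the ITT comparison with an exit SRS-2, they would dilute it. If removed after randomisation, that would depart from the declared principle and cost sample size and balance.

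**Working it through.** **Step 1. The plan's own figures.** Neither 27 nor 54 can be reproduced, because the documents contain no sample-size calculation. The check is therefore between sections.

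| Section | Enrolled | Randomised | Exposed or treated |
|---|---|---|---|
| 2 | up to 27 | 27 (in the RCT) | – |
| 4 | up to 54 | – | up to 27 |
| 6 | – | up to 27 | – |
| 9 | – | 54 | 54, for 8 weeks |

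Three readings can be tried:

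- *Up to 54 consent, screening follows, up to 27 are randomised and exposed.* This fits Sections 4 and 6 on number. It contradicts Section 9 and the consent trigger. It fits Section 2 only if enrolment there means something other than signing consent, which is Section 5's definition.
- *Up to 54 consent and all are randomised at consent.* This fits the trigger and the number randomised in Section 9. It contradicts Section 6 (up to 27 randomised). If only 27 are exposed, as in Section 4, it also contradicts Section 9, where all 54 are treated.
- *54 are randomised and treated.* This fits Section 9 alone.

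No reading satisfies every section.

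**Step 2. What the number conflict could mean for power (illustration).** Assumptions, none from the documents: true effect d = 0.8 SD (1.0 SD in brackets), two-sided alpha 0.05, and a two-sample t-test in place of the planned mixed model.

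The noncentrality is d / √(1/n₁ + 1/n₂), with n₁ + n₂ − 2 degrees of freedom.

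- 27 randomised, split 14:13: 0.8 / √(1/14 + 1/13) = 2.077, 25 df, critical value 2.060. Power is 0.515 (0.704).
- 54 randomised, 27:27: 0.8 / √(2/27) = 2.939, 52 df, critical value 2.007. Power is 0.822 (0.950).

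The difference detectable with 80% power is 1.12 SD with 27 and 0.78 SD with 54.

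**Step 3. What the timing wording could mean for power (same assumptions, 27 randomised 14:13).** Suppose k ineligible subjects are analysed with outcomes obtained, show no treatment effect and have the same SD. One such subject falls in the tPBM arm with probability 14/27 and then lowers that arm's mean effect by 1/14. The average loss is (14/27) × (1/14) = 1/27, so the effect becomes d × (1 − k/27).

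| Case | Power at 0.8 SD | Power at 1.0 SD |
|---|---|---|
| k = 0 | 0.515 | 0.704 |
| k = 1, averaged over arms | 0.485 | 0.671 |
| k = 2, averaged over arms | 0.456 | 0.637 |
| k = 3, averaged over arms | 0.427 | 0.602 |
| k = 1, in tPBM (d × 13/14) | 0.458 | 0.640 |
| k = 1, in sham | 0.515 | 0.704 |
| One excluded, not replaced (13:13 or 14:12) | 0.499 or 0.497 | 0.687 or 0.684 |
| Two excluded, not replaced (12:13 or 14:11) | 0.482 or 0.477 | 0.667 or 0.662 |

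**Step 4. Would moving the trigger settle every case?** No. Device training is at Week 0, so the device, and hence the allocation, probably precedes that visit in any event. The first scheduled examination of the application sites is also at Week 0, a pregnancy test is scheduled then, and the medication-stability criterion runs up to the start of treatment. Some criteria can therefore be finally confirmed only after allocation.

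**The case against.** The best reply is that the trigger is loose drafting and that the plan, read as a whole, screens first. Much supports this:

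- Section 4 includes only people who meet all criteria, and Section 5 bars those who do not qualify from participating.
- Criteria are applied before consent and reviewed again in the consent call.
- Section 6 bars a subject with a positive pregnancy test, and its text describes the eligibility work before it reaches the randomisation sentence.
- The washout text makes those subjects eligible only afterwards.
- Enrolling 54 to expose 27 presupposes losses before treatment.
- Section 3's maximum of 12 weeks equals four weeks of screening plus eight of treatment, which fits Section 9's eight weeks of treatment counted from randomisation.

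This stands as evidence of intent. A reader might infer that the plan has no eligibility condition at all, and the documents do not support that. What is missing is narrower: an express condition on allocation and mailing.

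A reader might also infer that ITT leaves out subjects later found ineligible. In its usual meaning it includes everyone randomised. The gap is that the plan does not define the set or reconcile it with removal for ineligibility.

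Nor does the wording imply bias in itself. Blinded removal on criteria fixed before randomisation need not bias the comparison.

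**Conclusion.** Two defects hold as written. The larger is the number: 27 or 54 randomised, together with 27 or 54 enrolled (Section 2 against Section 4). Under the assumed inputs this is the difference between about 51% and 82% power at 0.8 SD, or 70% and 95% at 1.0 SD. Sections 2, 4 and 6 favour 27 randomised and exposed. One might infer that 54 is simply an error, but without a derivation the documents do not establish it, and the sponsor must confirm.

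The smaller is the trigger. The eligibility work it appears to precede is real, but its practical effect is small if few subjects are affected: about 3 percentage points of power for one ineligible subject of 27 on average, and 6 for two. The documents give no rate of ineligibility after consent, so the actual size cannot be derived. It would also be wrong to assume that half of those randomised would never be exposed. That follows only from combining the literal trigger with Section 4's totals, and Section 6's own limit of 27 randomised contradicts it.

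The ITT part is mostly missing detail. It should be corrected with the rest, because some criteria can be settled only at Week 0 or at treatment start.

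**What to change.** 1. Reconcile Sections 2, 4, 6 and 9. State one number enrolled and one number randomised, with the sponsor confirming which was intended.
2. Replace the trigger in Section 6 with wording such as: *Once the screening-visit procedures are finished and every entry criterion that can be assessed at screening has been confirmed and documented, including completion of any washout, the subject is allocated to tPBM or sham and the assigned device is sent.*
3. Add a randomisation row to Table II.
4. State that criteria that can be checked only at Week 0 or at the start of treatment (site examination, repeat pregnancy test, medication stability) are confirmed then. Reconcile the exclusion list, the Baseline Visit text and Table II accordingly.
5. Define ITT in Section 9 as all randomised subjects in their assigned arm. Say that removal for ineligibility after randomisation does not take a subject out of that set.

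These are wording changes and need no new data. The downside is that mailing waits for the end of screening, up to four weeks from consent. It waits longer for washout subjects, for whom the plan sets no time limit.
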